10.2 Measurement Methods

Visually PET positive lymph nodes will be considered greater than blood pool (adjacent or mediastinal blood pool); PET positive bone lesions will be considered greater than physiologic bone marrow; PET positive prostate, prostate bed and visceral lesions will be considered greater than physiologic background activity of the involvement organ or anatomic site.

Sites of suspected metastatic disease will be graded as positive or negative on two separate analysis, for a more sensitive or specific visual read respectively.

10.3 Primary Endpoint

The primary endpoint is sensitivity and PPV on a per-patient and per-region-basis (Table 1) of ⁶⁸Ga-PSMA-11 PET for detection of tumor location confirmed by histopathology/biopsy.

Table 1: Region Definition

Region	Description
1	Prostate Bed
2	Pelvis outside of prostate bed including lymph nodes
3	Extrapelvic soft tissue, lymph nodes and organ metastases (non-bone)
4	Bone metastases

10.4 Secondary endpoints:

1. PPV and negative predictive value (NPV) on a per-patient and per-region-basis (Table 1) of ⁶⁸Ga-PSMA-11 PET for detection of tumor location confirmed by histopathology/biopsy and conventional imaging follow-up.
2. Sensitivity and specificity on a per-patient basis of ⁶⁸Ga-PSMA-11 PET for detection of tumor location confirmed by histopathology/biopsy and conventional imaging follow-up.
3. Detection rates on a per-patient basis of ⁶⁸Ga-PSMA-11 PET stratified by PSA value in ng/mL (0.2 to < 0.5; 0.5 to < 1.0; 1.0 to < 2.0; 2.0 to < 5.0; ≥ 5.0).

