10. MEASUREMENTS

10.1 Outcome Measures

The principal goal of this study is to compare, in the setting of suspected prostate cancer recurrence, the diagnostic performance of ^{68}Ga -PSMA-11 PET/CT in cases where conventional imaging for detecting recurrent prostate cancer is likely to have false negatives. Sites of suspected disease will be evaluated by ^{68}Ga -PSMA-11 PET/CT and conventional imaging by region for all patients. Specifically, it is hypothesized that the diagnostic performance of the ^{68}Ga -PSMA-11 PET/CT will be superior to anatomical imaging, and that ^{68}Ga -PSMA-11 PET/CT will provide complementary information.

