10.1.1 Primary Outcome

Primary Outcome Title: Confirmation of Prostate Cancer Recurrence

Description: Prostate cancer patients with suspected prostate cancer recurrence will be evaluated with ^{68}Ga -PSMA-11 PET/CT and conventional imaging. The outcome will be reported as the percentage of participants for whom tumor lesions are identified by ^{68}Ga -PSMA-11 PET/CT, and for whom tumor lesions are identified by histopathology/biopsy and/or conventional imaging follow-up. The outcome is reported as percentages without dispersion.

Time Frame: 1 year

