10.1.2 Secondary Outcomes

Secondary Outcome Title: ^{68}Ga -PSMA-11 PET/CT Sensitivity and Specificity by Participant

Description: The sensitivity and specificity of ^{68}Ga -PSMA-11 PET/CT for detection of tumor by participant will be determined, as confirmed by conventional imaging follow-up and/or histopathology/biopsy, within the following 1 year. The sensitivity and specificity of ^{68}Ga -PSMA-11 PET/CT for detection of tumor lesions is reported with the 95% confidence interval.

Time Frame: 12 months

Secondary Outcome Title: ^{68}Ga -PSMA-11 PET/CT Sensitivity and Specificity by Region

Description: The sensitivity and specificity of ^{68}Ga -PSMA-11 PET/CT for tumor detection by location will be determined, as confirmed by conventional imaging follow-up and/or histopathology/biopsy, within the following 1 year. The regions evaluated will be the prostate bed; pelvis outside of prostate bed including lymph nodes; extrapelvic soft tissue; lymph nodes; and organ metastases (non bone); and bone metastases. The

sensitivity and specificity of ^{68}Ga -PSMA-11 PET/CT for detection at the specified tumor locations is reported with the 95% confidence interval.

Time Frame: 12 months

Secondary Outcome Title: ^{68}Ga -PSMA-11 PET/CT Predictive Value by Participant

Description: The predictive value of ^{68}Ga -PSMA-11 PET/CT for detection of tumor, as confirmed by conventional imaging follow-up and/or histopathology/biopsy, within the following 1 year, is assessed by participant. Positive predictive value (PPV) is the probability that participants identified by ^{68}Ga -PSMA-11 PET/CT as having prostate cancer recurrence, do have prostate cancer recurrence. Negative predictive value (NPV) is the probability that participants not identified by ^{68}Ga -PSMA-11 PET/CT as having prostate cancer recurrence, do not have prostate cancer recurrence. The outcome is reported as the PPV and the NPV of ^{68}Ga -PSMA-11 PET/CT for confirmation of prostate cancer recurrence by participant, with 95% confidence interval.

Time Frame: 12 months

Secondary Outcome Title: ^{68}Ga -PSMA-11 PET/CT Predictive Value by Region

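### Sections 10.1.1 and 10.3 name different primary endpoints and nothing ranks them; separately, 11.3.1 as written leaves out the PET-negative participants that the accuracy measures need

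*Combined protocol and SAP*

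**What the plan says.** Two current sections each name the primary.

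- **10.1.1**: "The outcome will be reported as the percentage of participants for whom tumor lesions are identified by" PSMA-11 PET/CT, "and for whom tumor lesions are identified by histopathology/biopsy and/or conventional imaging follow-up". It adds: "The outcome is reported as percentages without dispersion".
- **10.3**: "The primary endpoint is sensitivity and PPV on a per-patient and per-region-basis (Table 1) of" PSMA-11 PET, confirmed by histopathology or biopsy only.

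The secondary lists follow the same split. Section 10.1.2 puts sensitivity among the secondary outcomes, "for detection of tumor by participant will be determined, as confirmed by conventional imaging follow-up and/or histopathology/biopsy, within the following 1 year". It does the same for PPV ("Positive predictive value (PPV) is the probability that participants identified by" PET as recurrent truly are so). Section 10.4, which belongs with 10.3, lists as secondary "PPV and negative predictive value (NPV) on a per-patient and per-region-basis (Table 1) of" PSMA-11 PET, this time against histopathology/biopsy *and* imaging follow-up. Section 2.5 item 12 says that clinical follow-up is collected for the secondary endpoints.

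The synopsis and 11.3.2 plan 95% confidence intervals for the percentage of patients with true lesions and for sensitivity and specificity. Hypothesis 1 in the synopsis sets 30% for patients with lesions detected on PET/CT; hypothesis 2 sets at least 70% for sensitivity and specificity. Section 11.3.1 defines the analysis population as the lesions that PET/CT identifies. Section 11.4 expects about ±7 points for a 30% discovery rate in 200 patients and about ±10 points for sensitivity and specificity.

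**The concern.** The two primaries differ in measure, unit and reference standard. The standards are not interchangeable: 10.1 places the study where "conventional imaging for detecting recurrent prostate cancer is likely to have false negatives", and the composite standard leans partly on conventional imaging follow-up. With no ranking, the same data can yield different primary results, and nothing fixes in advance which one is reported.

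The analysis population is a second defect. Sensitivity needs missed disease in its denominator, and specificity and NPV need PET-negative units. A population made up only of PET-identified lesions has neither.

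**Working it through.** **1. The sections side by side**

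| | 10.1.1 | 10.3 | 11.3.2 |
|---|---|---|---|
| Measure | Percentage of participants (one joint percentage, or two) | Sensitivity and PPV | True-lesion percentage; sensitivity; specificity |
| Unit | Participant | Patient and four Table 1 regions | Patient for the percentage; otherwise not stated |
| Reference | Histopathology/biopsy and/or imaging follow-up | Histopathology/biopsy | Not stated |
| Interval | No dispersion | Not stated | 95% CI |

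Count for 10.3: 2 measures × (1 patient level + 4 regions) = 10 estimates.

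Two hierarchies emerge. In 2.5 item 12, 10.3 and 10.4, histology is primary and follow-up secondary. In 10.1.1 and 10.1.2, the percentage is primary, and sensitivity and PPV are secondary against the composite standard.

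**2. The plan's own precision figure**

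Half-width = 1.96 × √(p(1 − p)/n). At p = 0.30 and n = 200: 1.96 × √(0.21/200) = 6.4 points. The exact interval for 60/200 is 23.7% to 36.9%. The maximum, at p = 0.50, is 6.9 points. The stated ±7 therefore reproduces for any participant percentage on 200.

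**3. Section 11.3.1 taken literally**

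Every unit is PET-positive, so FN = 0 and TN = 0. For illustration, take 60 units of which 70% are true: TP = 42, FP = 18.

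- Sensitivity = 42/(42 + 0) = 100%.
- Specificity = 0/(0 + 18) = 0%.
- NPV = 0/0, not estimable.
- PPV = 42/60 = 70%, the only usable measure, and one that 11.3.2 does not list.

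**4. How far the two primaries can differ**

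Set sensitivity and specificity at 70% (hypothesis 2 at its floor), verify everyone, and let p be the share truly recurrent (assumed range). Detected = 0.7p + 0.3(1 − p) = 0.3 + 0.4p. Detected and confirmed = 0.7p. PPV = 0.7p/(0.3 + 0.4p).

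| p | 10.1.1, joint | 10.1.1, as two percentages (detected / reference-positive) | 10.3 sensitivity | 10.3 PPV |
|---|---|---|---|---|
| 20% | 14% | 38% / 20% | 70% | 37% |
| 50% | 35% | 50% / 50% | 70% | 70% |
| 80% | 56% | 62% / 80% | 70% | 90% |

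**5. The 30% target**

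At 70%/70%, a confirmed rate of 30% needs p = 0.30/0.70 = 0.429, which means 0.3 + 0.4 × 0.429 = 47% detected. Conversely, fix detection at 30% with sensitivity 70%:

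- Specificity 80%: 0.2 + 0.5p = 0.30, so p = 0.20 and confirmed = 14%.
- Specificity 90%: 0.1 + 0.6p = 0.30, so p = 0.333 and confirmed = 23%.

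**6. Precision if 10.3 is the primary**

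Section 11.4 gives none for PPV or regions. Take 60 PET-positive men (30% of 200), PPV 70%, and an assumed share biopsied:

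| Biopsied | n | Half-width (points) |
|---|---|---|
| 100% | 60 | 11.6 |
| 50% | 30 | 16.4 |
| 30% | 18 | 21.2 |
| 20% | 12 | 25.9 |

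The ±10 for sensitivity has no stated denominator. Solving n = p(1 − p)(1.96/0.10)² gives 81 reference-positive men at 70%, 62 at 80% and 35 at 90%. Under 10.3 all of them must be histology-positive.

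**The case against.** **Single-arm estimation, most measures reported anyway.** There is no alpha or decision rule, and 10.1.2 already gives PPV, NPV and regional accuracy with 95% CIs and a named standard, so much of what 11.3.2 omits is covered. This stands and limits the harm. It does not cover histology-only sensitivity and PPV, which appear only as the primary in 10.3.

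**Section 11.3.1 is loose wording.** This largely stands. Section 10.1 evaluates sites by region for all patients, 10.1.2 defines NPV on participants whom PET did not identify, and 11.4 uses 200 patients as its denominator. A reader might infer that the trial cannot estimate sensitivity or specificity, or that the participant percentage has no denominator. The documents do not support that, because PET-negative men are plainly meant to be analysed. The section is still wrong as written.

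**Item 12 of 2.5 as a further inconsistency.** A reader might count it as one. It agrees with 10.3 and 10.4, and conflicts only if 10.1.1 is the primary.

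**The absence of dispersion in 10.1.1 as a contradiction of the planned CIs.** This is not established. The detection-rate outcome in 10.1.2 lists SD and CI as separate items, so dispersion may mean SD only.

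**The illustration in step 4.** A detection rate and a PPV differ by definition, and one shared truth with full verification is assumed. The table therefore shows that the headline changes; it does not measure the gap between the composite and histology-only standards. Both hypotheses are also held at their floors.

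**Conclusion.** The point holds on the current text. Two different primaries are named and not ranked, 11.3.2 fully matches neither, and the 30% target is set for detected lesions while 11.3.2 reports true ones. In the illustration the joint 10.1.1 percentage runs from 14% to 56%, with 10.3 sensitivity fixed at 70% and PPV running from 37% to 90%. Those figures rest on assumed prevalences of 20% to 80%, and the PPV half-widths of 11.6 to 25.9 points on assumed biopsy shares. The endpoint conflict and the 11.3.1 result need no such assumption.

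Three stronger readings go too far. The sample-size arithmetic is not shown to be wrong: ±7 reproduces, and ±10 can be neither confirmed nor refuted without a denominator. The documents do not show that the confirmed detection rate is the intended primary: hypothesis 1 and the discovery rate in 11.4 point to detected lesions, while 2.5, 10.3 and 10.4 point to histology. Nor is there evidence of intent to select a result; the text only leaves room for it.

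**What to change.** 1. Name one primary, with one measure, unit and reference standard, identically in the synopsis, 10.1.1, 10.3 and 11.3.2, and list the other as secondary. The choice is the sponsor's.
   - If 10.1.1 is kept: say whether it is one joint percentage or two, report the 95% CI that 11.3.2 already plans, and amend 2.5 item 12 so that follow-up also serves the primary.
   - If 10.3 is kept: add PPV, regions and the histology-only standard to 11.3.2, and state the expected precision in 11.4.
2. State whether the 30% applies to the detected or the confirmed rate, and align hypothesis 1, 11.3.2 and 11.4.
3. Change 11.3.1 to all scanned participants, and to all four Table 1 regions per participant for region analyses. Take accuracy measures from those with a reference-standard result, PET-negatives included, and report how many are unverified.
4. Reconcile *and/or* in 10.1.2 with *and* in 10.4.

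Cost: a wording amendment with no new scans, visits or change in sample size. One of the two current primaries loses primary status. If the composite standard is chosen, the result depends partly on conventional imaging, which 10.1 expects to miss disease; if histology alone is chosen, precision depends on how many men are biopsied.

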All participants tolerated the procedure without immediate or delayed (up to 7 days) complaints or complications. The areas with the highest ⁶⁸Ga-PSMA-11 accumulation are the lacrimal gland (mean SUV_{max}: 9.3 \pm 3.3 [range: 4.6 to 14.9] and SUV_{mean}: 5.2 \pm 2.3 [range: 2.5 to 8.8]), the parotid gland (mean SUV_{max}: 14.2 \pm 2.6 [range: 9.9 to 19.1] and SUV_{mean}: 11.8 \pm 2.6 [range: 7.2 to 16.1]), the submandibular gland (mean SUV_{max}:

16.8 ± 3.3 [range: 12.3 to 22.7] and SUV_{mean} : 13.5 ± 2.9 [range: 9.8 to 18.1]), small intestine (mean SUV_{max} : 14.6 ± 4.6 [range: 8.2 to 23.4] and SUV_{mean} : 11.0 ± 3.9 [range: 5.6 to 18.5]), kidney (mean SUV_{max} : 35.1 ± 9.9 [range: 14.4 to 46.2] and SUV_{mean} : 25.8 ± 7.5 [range: 12.0 to 36.0]) and bladder (mean SUV_{max} : 35.0 ± 24.7 [range: 9.6 to 78.5] and SUV_{mean} : 26.5 ± 17.4 [range: 7.8 to 67.9]), while moderate uptake was noted in the sublingual gland (mean SUV_{max} : 5.0 ± 2.4 [range: 1.9 to 10.6] and SUV_{mean} : 3.3 ± 1.6 [range: 1.5 to 7.1]), liver (mean SUV_{max} : 6.0 ± 1.3 [range: 4.1 to 9.0] and SUV_{mean} : 4.1 ± 0.8 [range: 3.2 to 5.7]) and spleen (mean SUV_{max} : 8.0 ± 3.3 [range: 2.6 to 12.3] and SUV_{mean} : 6.4 ± 2.7 [range: 2.0 to 10.5]). Other tissues analyzed had low ^{68}Ga -PSMA-11 uptake, with SUV_{mean} of less than 1.7. There were no differences between the ^{68}Ga -PSMA-11 biodistribution at 45 minutes post-injection among the 10 participants (Figure 2). The pattern of ^{68}Ga -PSMA-11 uptake is similar to previous reports.

^{68}Ga -PSMA-11 uptake outside the expected physiologic biodistribution

There were 45 areas of high ^{68}Ga -PSMA-11 uptake that corresponded on the CT images to bone marrow ($n = 13$), retroperitoneal lymph nodes ($n = 12$), mediastinal lymph nodes ($n = 8$), pelvic lymph nodes ($n = 9$), seminal vesicle ($n = 2$), subclavian lymph node ($n = 1$).

[figure not shown]

Figure 1: Maximum intensity projection (MIP) images from 10 participants in the pilot study conducted at Stanford University.

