11.3 Key variables

11.3.1 Analysis Population

All lesions identified by ⁶⁸Ga-PSMA-11 PET/CT.

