11.3.2 Analysis Plan

We will calculate point estimates and 95% confidence intervals for:

1. Percentage of patients who had true lesions.
2. Sensitivity and specificity of ^{68}Ga -PSMA-11 PET/CT.

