11.4 Sample Size

We expect to recruit 200 patients over the course of this trial. The number of lesions cannot be predicted at this time, however, if our expectation of a 30% discovery rate is correct, the resulting confidence interval would be roughly ± 7 percentage points, and confidence intervals for specificity/sensitivity would be roughly ± 10 percentage points.

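### Section 11 fixes neither the unit nor a clustering rule for sensitivity, specificity and PPV; intervals over lesions, or over regions pooled across men, would be too narrow if computed as if independent

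*Combined protocol and SAP*

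**What the plan says.** Three units appear in the protocol.

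- **Patient and region.** Section 10.3: "The primary endpoint is sensitivity and PPV on a per-patient and per-region-basis (Table 1"). Table 1 defines four regions. Section 10.1.2 asks for sensitivity, specificity, PPV and NPV by participant and by region, each with a 95% interval. Neither section says whether by-region means four separate estimates or one estimate pooled over regions.
- **Lesion.** Section 11.3.1 gives the only analysis population: "All lesions identified by" the study PET/CT.
- **Not named.** Section 11.3.2 reads "We will calculate point estimates and 95% confidence intervals for" two items: the share of men with true lesions, and sensitivity and specificity. The second item has no unit, and no interval method is given for either.

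On precision, section 11.4 starts from men ("We expect to recruit 200 patients over the course of this trial"). It then says "The number of lesions cannot be predicted at this time" and continues that "if our expectation of a 30% discovery rate is correct, the resulting confidence interval would be roughly ± 7 percentage points", and that "confidence intervals for specificity/sensitivity would be roughly ± 10 percentage points". The last figure has no denominator.

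The pilot in section 2.1 shows that one man can supply several units. It enrolled ten men and reports "There were 45 areas of high" uptake outside the normal distribution. Section 5.3 has three readers interpret the PET data and gives no rule for combining their reads.

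No section mentions within-man correlation, GEE, a cluster bootstrap or a robust variance.

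**The concern.** Lesions and regions in the same man share his tumour biology, PSA, scan, readers and reference work-up, so their results tend to agree. The usual binomial interval counts each as a separate piece of evidence and so overstates the information.

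An analyst who follows section 11 literally would take the lesion set from 11.3.1 and put an ordinary 95% interval on a proportion of lesions. An analyst who reads the per-region endpoint in 10.3 as one pooled figure would do the same over man-regions. Nothing in the plan prevents either, and the choice could be made after the data are seen. The stake is the stated precision of whichever pooled region or lesion results are reported, and per-region sensitivity and PPV are part of the primary endpoint.

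**Working it through.** **1. The plan's own figures.** For 30% of 200 men, the half-width is 1.96 × √(0.30 × 0.70 / 200) = 6.35 points. The Clopper-Pearson interval is 23.7% to 36.9%. The stated figure of roughly 7 is therefore reproduced on a simple per-patient basis, where no clustering arises.

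The figure of roughly 10 cannot be traced. At a proportion of 70% it needs 0.21 × (1.96 / 0.10)² = 80.7, so 81 independent units. If 30% of the men have disease, 60 men give ± 11.6 for sensitivity and 140 men give ± 7.6 for specificity. These bracket 10, but the plan does not say what was counted.

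**2. Inputs for the clustering check.**

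- Units per man, *m*: 4 is the Table 1 maximum. The pilot gives (13 + 12 + 8 + 9 + 2 + 1) / 10 = 45 / 10 = 4.5 lesions. Values of 1.5 and 2 are assumed, because sensitivity counts only diseased regions and PPV only PET-positive ones.
- Within-man correlation, ρ: not in the documents; 0.1, 0.3 and 0.5 are assumed.

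**3. Formulas.** Design effect DE = 1 + (*m* − 1)ρ. The correct half-width is √DE times the naive one. True coverage of a naive 95% interval = 2Φ(1.96 / √DE) − 1.

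| Units per man | DE at ρ = 0.1 / 0.3 / 0.5 | Widening needed (×) | True coverage of naive 95% interval |
|---|---|---|---|
| 1 (one region alone, or per patient) | 1 / 1 / 1 | 1 | 95% |
| 1.5 | 1.05 / 1.15 / 1.25 | 1.02 / 1.07 / 1.12 | 94.4% / 93.2% / 92.0% |
| 2 | 1.10 / 1.30 / 1.50 | 1.05 / 1.14 / 1.22 | 93.8% / 91.4% / 89.0% |
| 4 | 1.30 / 1.90 / 2.50 | 1.14 / 1.38 / 1.58 | 91.4% / 84.5% / 78.5% |
| 4.5 | 1.35 / 2.05 / 2.75 | 1.16 / 1.43 / 1.66 | 90.8% / 82.9% / 76.3% |

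**4. In percentage points, for the lesion case.** Assume 60 PET-positive men (30% of 200) with 4.5 lesions each, 270 lesions in all, and a true proportion of 70%. The naive half-width is 1.96 × √(0.21 / 270) = 5.5 points. Multiplied by √DE it becomes 6.4, 7.8 or 9.1 points at ρ = 0.1, 0.3 or 0.5.

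**5. Simulation (beta-binomial, 5,000 runs, true proportion 70%, ρ = 0.1 / 0.3 / 0.5).**

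- Four regions pooled over 200 men: naive coverage 91% / 84% / 78%; cluster-robust 95% / 95% / 94%.
- One region alone: naive coverage 94% at each ρ.
- Lesions in 60 men, counts 1 + Poisson(3.5): naive 89% / 81% / 72%; cluster-robust 94% at each ρ.
- A separate simulation with more widely spread lesion counts (geometric, mean 4.5) gives naive coverage of 86% / 73% / 64%. The lesion result therefore depends on the assumed spread of counts as well as on ρ.

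**The case against.** A reader might infer that the plan pools regions and lesions over men with simple binomial intervals, so that the primary per-region intervals will be too narrow. The documents do not support that.

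- No section says regions are pooled. Section 10.1.2 lists the regions and ties the results to those locations, which fits one estimate per region with at most one unit per man. Read that way, an ordinary interval is adequate.
- No interval method is named. The one traceable calculation, ± 7 at 30% of 200, is per patient, where a binomial interval is right. It says nothing about how regions would be handled.
- No outcome or endpoint in section 10 is per lesion. Lesions enter as a unit only through 11.3.1 and the remark in 11.4.
- The pilot's 4.5 lesions per man came from men with PSA 2.6 to 36.4 (mean 12.4), while section 3.1 admits men after prostatectomy with PSA just above 0.2. It also counts areas of uptake, whereas 10.3 requires confirmation by histopathology or biopsy. Fewer units per man are likely, and at 1.5 to 2 the loss is small.

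A reader might also infer that a lower limit could falsely appear to clear the hypothesised 70%. That hypothesis names no unit and carries no lower-limit decision rule, and if it is per patient, clustering over regions or lesions does not touch it.

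All of this stands, and it limits the point to a conditional one. It does not remove it: 11.3.1 still makes lesions the analysis population, 10.3 leaves separate or pooled open, and no clustered method is given if units are pooled.

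**Conclusion.** The point holds in conditional form. The plan leaves open the unit for sensitivity, specificity, PPV and NPV, and whether regions are pooled. An interval over lesions or pooled regions computed as if independent would under-cover at any positive within-man correlation.

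The size runs from slight to material. At an assumed correlation of 0.1 to 0.5, nominal 95% coverage is really about 94% to 89% with 1.5 to 2 units per man, 91% to 78% with all four regions, and 91% to 76% with 4.5 lesions per man, lower still if lesion counts vary widely. The last two cases are a maximum and a probable upper figure. The correlation and the number of confirmed units per man are both assumptions.

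The per-patient intervals and the ± 7 figure are sound on this point. So are intervals for each region on its own, provided the three reads are first reduced to one result per man and region.

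**What to change.** Amend 11.3.1 and 11.3.2 to say, in substance:

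- The units of analysis for sensitivity, specificity, PPV and NPV are the patient, and the region within the patient.
- The four Table 1 regions are reported separately, each with an ordinary binomial 95% interval.
- The 95% interval for any estimate pooled over regions, lesions or reads comes from a patient-level cluster bootstrap, or from GEE with robust variance clustered on the man, so that all his units are kept together.

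Both units can stay primary as 10.3 has them; the change does not require ranking one above the other.

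The cost is a few sentences and a few lines of code, with no new data. Pooled intervals become wider: by 2% to 22% at 1.5 to 2 units per man, and by 16% to 66% at 4.5, over the assumed correlations. In the simulations in the working, cluster-robust intervals brought coverage back to 94% to 95%. They were not tried with fewer than 60 men, so a pooled estimate resting on far fewer men would need its own check.
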